Appendix 3: Overview of Friendship Bench lay counselor training sessions¹

	Self-care strategies for counselors
Session 5 (9 AM – 5PM)	 Review of prior sessions Healthy and unhealthy relationships Working with clients who have experienced gender-based violence or fear violence from a partner Discussing sexual behavior and PrEP use Urine point-of-care assay training Summary and questions

SRQ-20=Self Reporting Questionnaire – 20 item; PrEP=pre-exposure prophylaxis ¹Training session outline and content will be informed by the materials used in the primary Friendship Bench intervention study in Zimbabwe and other Friendship Bench implementation studies in sub-Saharan Africa ²Each session will last one day and will be conducted consecutively during a 1-week period

Appendix 4: Schedule of Study Visits and Procedures

	ENROLLMENT	WEEK 2	WEEK 4	WEEK 8	WEEK 12			
Administrative and Behavioral Evaluations/Procedures								
Informed Consent	X							
Collect/update locator information	X		x					
Apply inclusion/exclusion criteria, including the SRQ-20	X							
Randomization	X							
Collect demographics, behavioral, and psychosocial data, including the SRQ-20	X		x		Х			
PrEP adherence assessment via self-report			x		X			
Youth Friendship Bench SA counseling	X	X1	x	X1	Х			
Standard-of-care mental health service delivery	X		x		Х			
Assess any SAEs		x	x	X	X			
Laboratory Evaluation/Procedures								
Urine sample collection for TFV testing using a point-of-care assay			X		X			
PrEP counseling based on urine TFV drug levels			x		Х			

TFV=tenofovir; PrEP=pre-exposure prophylaxis; SAE=serious adverse event; SRQ-20=self-reporting questionnaire 20-item ¹Youth Friendship Bench SA sessions could be conducted remotely via phone

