8.3.3. Week 2 Visit – Youth Friendship Bench SA participants only

- 1. Only participants randomized to the Youth Friendship Bench SA intervention will complete this visit, which will be their 2nd counseling session. This session may be conducted via phone.
- Schedule participant for their Week 4 visit in 14 days. The Week 4 visit will be scheduled as an in-person session for a time when they are able to return to the clinic.

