8.3.4. Week 4 Visit

- 1. Confirm consent
- 2. Confirm locator information and update as needed
- 3. Collect psychosocial and behavioral data additional data (see Section 6).
- 4. Assess symptoms of common mental disorders
 - a. All participants will receive assessments per APC guidelines and referrals as needed. They will also complete the SRQ-20 with the lay counselor.
 - b. Participants Youth Friendship Bench SA arm will complete their 3rd counseling session.
- 5. Schedule participant's next visit
 - a. Standard-of-care participants will be scheduled for their Week 12 visit in 60 days.
 - b. Youth Friendship Bench SA participants will be scheduled for their Week 8 visit in 30 days. They will be offered the option to complete the Week 8 visit in-person or remotely (over the phone).
- 6. All participants will be asked to provide a urine sample for the tenofovir (TFV) point-of-care (POC) assay. Urine POC assay testing and drug-level feedback counseling based on assay results will be conducted by the lay Youth Friendship Bench SA for participants in both arms and proceed as described in Section 5.1.2. The urine assay results will be used for research purposes only and will not be included in the clinic record.
- 7. Schedule in-depth interviews for AGYW between the Week 4 and Week 12 study visit.

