8.3.5. Week 8 Visit – Youth Friendship Bench SA participants only

- Participants randomized to the Youth Friendship Bench SA intervention will complete their 4th counseling session at this visit. This session may be conducted via phone
- 2. Schedule participant for their Week 12 visit in 30 days.
- Schedule participants for optional group session (either in person or via WhatsApp as they
 prefer, for between the Week 8 and 12 visits with the exact timing depending on availability of
 participants and enrollment accrual rates).

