9.3. Adverse Event Definition and Reporting

For the purposes of this study, only serious adverse events (SAEs) and adverse events of special interest (AESIs) will be recorded. These will be summarized by arm, as a secondary outcome of our study. SAEs are defined as those events that result in death, are life-threatening, require inpatient hospitalization or prolongation of existing hospitalization, and/or result in persistent or significant disability/incapacity. AESIs are considered reports of self-harm or self-injury.

With appropriate permission of the participant, whenever possible, records from all non-study medical providers related to SAEs will be obtained and required data elements will be recorded

on study CRFs. All participants reporting an AE will be followed clinically, until the AE resolves (returns to baseline) or stabilizes.

Site staff will also report information regarding SAEs to their IRB or other local regulatory agencies in accordance with all applicable regulations and local IRB requirements.

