11.0 STATISTICAL CONSIDERATIONS

11.1. Review of Study Design

At enrollment, women will be randomized 1:1 to either the standard-of-care mental health services (screening, referral, etc.) plus the Youth Friendship Bench SA intervention or standard-of-care services alone. Participants receiving the Youth Friendship Bench SA will complete individual counseling sessions at Enrollment, Week 2 (option to be conducted remotely), Week 4, Week 8 (option to be conducted remotely), and Week 12. They will also be invited to participate in an in-person or virtual group-based session (between their Week 8 and 12 visits, with the exact timing depending on participant availability and participant accrual rate) focused on an economic empowerment activity like job and school applications. Participants in the standard-of-care arm will complete visits at Enrollment, Week 4, and Week 12. The co-primary outcomes are: 1) the proportion with PrEP adherence measured by TFV levels detected in urine using a POC assay at Week 12 and 2) the proportion with reduced symptoms of common mental disorders measured by the SRQ-20 at Week 12. For the PrEP adherence measure, we will utilize urine TFV levels to assess PrEP dosing in the prior 4-7 days. The assay uses a threshold

of 1500 ng/mL to categorize participants as adherent as this was associated with daily dosing over 4-7 days in directly observed therapy.¹¹²

We will conduct all randomizations using a SAS-based computer-generated randomization scheme developed by the study data manager. The site sub-investigator will conduct the randomizations and fill out a randomization log which will be reviewed by the study data manager during visits to the study site. The identity of participants in each of the arms will not be known to investigators and access to the randomization code will be strictly controlled. The study blind will be broken only on completion of the clinical study and after the database has been locked. The study investigators will receive the unblended results only after that point.

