- SAEs (including events that result in death, are life-threatening, require inpatient hospitalization or prolongation of existing hospitalization, and/or result in persistent or significant disability/incapacity) and adverse events of special interest (reports of self-harm or self-injury).
- We will analyze qualitative data (in-depth interviews, clinic observation field notes) using an inductive and deductive coding approach and will use descriptive statistics to summarize quantitative data on intervention acceptability, feasibility, and appropriateness and SAEs and AESIs.

Secondary Analysis 5: To monitor and describe the occurrence of serious adverse events over the study (defined as those events that result in death, are life-threatening, require inpatient hospitalization or prolongation of existing hospitalization, and/or result in persistent or significant disability/incapacity) plus adverse events of special interest (reports of self-harm or self-injury).

Statistical analyses:

1) We will compute descriptive statistics to describe the occurrence of serious adverse events and adverse events of special interest. For the full study population, we will compute means, standard deviations, medians, and inter-quartile ranges for each of the adverse events that may occur. Chi-squared tests will be used to assess differences in adverse study events across meaningful groupings, such as between study arms.

Exploratory Objective 1: To explore mediators and moderators of the Youth Friendship Bench SA intervention effect on PrEP adherence.

- Mediators and moderators of the Youth Friendship Bench SA intervention effect on PrEP adherence at 12 weeks
- Covariate characteristics assessed at baseline and follow-up may include Sociodemographic characteristics; sexual behaviors; gender-based violence (GBV); symptoms of common mental disorders; self-esteem; intervention acceptability, feasibility, and appropriateness; and level of engagement with the intervention.

Exploratory Objective 2: To explore mediators and moderators of the Youth Friendship Bench SA intervention effect on symptoms of common mental disorders.

• Mediators and moderators of the Youth Friendship Bench SA intervention effect on symptoms of common mental disorders at 12 weeks

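### Adverse events are scheduled to be asked about four times in the intervention arm and twice in standard of care, yet the SAP tests them between arms without allowing for this

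*Protocol*

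**What the plan says.** **Schedule.** Protocol Appendix 4 marks "Assess any SAEs" at Weeks 2, 4, 8 and 12, with no arm restriction on that row.

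**Who attends.** Of Week 2, Protocol 8.3.3 says "Only participants randomized to the Youth Friendship Bench SA intervention will complete this visit". Protocol 8.3.5 is headed as an intervention-only visit and says of Week 8: "Participants randomized to the Youth Friendship Bench SA intervention will complete their 4th counseling session at this visit". For the comparator, Protocol 11.1 says "Participants in the standard-of-care arm will complete visits at Enrollment, Week 4, and Week 12", and Protocol 8.3.4 adds "Standard-of-care participants will be scheduled for their Week 12 visit in 60 days".

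**What counts.** Protocol 9.3 limits recording to SAEs and adverse events of special interest, summarized by arm as a secondary outcome. It defines the latter by disclosure: "AESIs are considered reports of self-harm or self-injury".

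**Analysis.** SAP Secondary Analysis 5 says "Chi-squared tests will be used to assess differences in adverse study events across meaningful groupings, such as between study arms". It does not limit the comparison to visits that both arms attend, and it does not take account of where an event came to light.

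**Other contact.** Protocol 7.1 gives the intervention arm five individual sessions of up to 60 minutes and an optional group session. Protocol 8.4 reserves rapid follow-up of missed visits and SMS reminders for that arm.

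**The concern.** Ascertainment differs by arm by design. Every other outcome row in Appendix 4 (SRQ-20 and psychosocial data, self-reported adherence, urine tenofovir) is marked only at visits both arms attend. Safety is the exception.

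This matters most for self-harm, which enters the data only if a woman is asked and chooses to tell. The asymmetries point the same way: more scheduled assessments, longer conversations about mental health, and tracing after a missed visit. Protocol 8.3.7 also asks about interim clinic visits at each study visit, so that question too is put more often in the intervention arm.

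In a trial of a mental health intervention, self-harm is likely to be the first safety result a reader looks for. If the intervention arm shows an excess, the planned data could not tell a real excess from one produced by asking more often. A harmless intervention could look harmful, or a real harm could be explained away.

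**Working it through.** No document gives a power, event rate or disclosure rate for the safety comparison, so there is no stated figure to reproduce.

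**Step 1: count the assessments.** Weeks marked in Appendix 4, set against attendance (Protocol 8.3.3, 8.3.5, 11.1):

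| Week | Intervention | Standard of care |
|---|---|---|
| 2 | yes | no visit |
| 4 | yes | yes |
| 8 | yes | no visit |
| 12 | yes | yes |
| Total | 4 | 2 |

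**Step 2: check calendar time.** From the scheduling intervals in Protocol 8.3.2 to 8.3.5, the intervention arm runs 14 + 14 + 30 + 30 = 88 days and standard of care 30 + 60 = 90 days. The arms differ in number of contacts, not in time covered.

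**Step 3: illustrate the effect on the risk ratio.** Assume the same true risk in both arms and a probability *d* that any one assessment detects an event. Both are assumptions.

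- Model A: every event gets all the arm's assessments. Detection is 1 − (1 − d)⁴ against 1 − (1 − d)². At d = 0.3 this is 0.760 / 0.510 = 1.49.
- Model B: events are uniform over 12 weeks and only later assessments can detect them. Intervention: (2/12)[1 − (1 − d)⁴] + (2/12)[1 − (1 − d)³] + (4/12)[1 − (1 − d)²] + (4/12)d. Standard of care: (4/12)[1 − (1 − d)²] + (8/12)d.

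| d | A: detected | A: ratio | B: detected | B: ratio |
|---|---|---|---|---|
| 0.3 | 0.760 v 0.510 | 1.49 | 0.506 v 0.370 | 1.37 |
| 0.5 | 0.938 v 0.750 | 1.25 | 0.719 v 0.583 | 1.23 |
| 0.7 | 0.992 v 0.910 | 1.09 | 0.864 v 0.770 | 1.12 |
| 0.9 | 1.000 v 0.990 | 1.01 | 0.963 v 0.930 | 1.04 |

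**Step 4: effect on the test.** Exact binomial enumeration of the uncorrected chi-squared test, with an assumed two-sided alpha of 0.05 (the SAP states none for this test). There are 110/2 = 55 per arm, or about 47 at 85% retention (0.85 × 55 = 46.75). True risk is equal in the two arms.

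- Complete detection in both arms: false-positive rate 0.045 to 0.059.
- 5% true risk: about 0.05 or below throughout.
- 10% true risk: at most 0.088 (47 per arm, d = 0.3, Model A).
- 20% true risk: at most about 0.12 (d = 0.3, Model A), almost all of it against the intervention.

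**Step 5: test the tempting remedy of excluding events first disclosed at Week 2 or Week 8.** Use Model B with complete detection. The intervention arm then keeps only events arising in Weeks 2–4 and 8–12, that is (2 + 4)/12 = 50%. Standard of care keeps 100%, so the apparent risk ratio is 0.50 with no true difference. At d = 0.9, 0.5 and 0.3 it is about 0.53, 0.70 and 0.80. That exclusion would hide harm.

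**The case against.** Much can be said for the plan.

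- **The row names SAEs only.** Deaths, hospitalizations and disability can largely be recovered by recall at Weeks 4 and 12, and both arms cover the same period. This stands, and it confines the worry mainly to self-harm. No self-harm assessment is separately scheduled, and the visit lists for Weeks 2 and 8 mention no safety elicitation. Extra disclosure in counseling is therefore plausible rather than prescribed.
- **Standard of care is not without contact.** At Weeks 4 and 12 both arms have the guideline assessment, the SRQ-20 with a lay counselor, psychosocial data collection and urine-result counseling. Protocol 9.1 applies the symptom-change question and suicidality procedures to everyone, and interim contacts are open to both arms. This also stands. It narrows the gap but does not close it.
- **The objective is descriptive.** Protocol 6.2 and 11.4.3 speak of describing events, and unequal contact is inherent in adding counseling to usual care. That is fair, but the SAP adds a formal test between arms, and even a descriptive table by arm invites the same comparison.

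A reader might infer that self-harm reports would nearly double in the intervention arm. That takes, for example, a 20% true risk with 90% disclosure against 50%: 55 × 0.20 × 0.90 = 9.9 against 55 × 0.20 × 0.50 = 5.5. None of these rates is in the documents, and the disclosure rates do not follow from the 4-to-2 schedule. Protocol 7.3.3 also excludes women who report suicidal intent or self-harm at entry, so 20% may be high.

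**Conclusion.** The point holds as a structural one. Scheduled assessments are 4 against 2, self-harm is counted on report, and the planned between-arm test ignores the source of the report. With equal true risk, the expected direction is more recorded events in the intervention arm.

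The size cannot be established from the documents. The range of 1.01 to 1.49 applies to assumed detection of 0.3 to 0.9 per assessment, taken as equal in the two arms. It illustrates the schedule alone and is not a bound. At low event rates the problem is a biased estimate rather than an inflated test. A reader might infer that a false harm signal is likely; the false-positive rate rises to about 0.12 only with high risk and poor detection together, so the documents do not support that.

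This affects a secondary safety outcome, not either co-primary endpoint. It merits a cheap improvement.

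**What to change.** 1. **Common question.** At Weeks 4 and 12, ask both arms the same SAE and self-harm question covering the whole period since the last common visit (enrollment or Week 4). Tell women to include anything already mentioned. The existing SRQ-20 follow-up items (Appendix 2) cannot serve, because they ask about thoughts and about attempts at any time, not about self-injury in the period.
2. **Basis of comparison.** In SAP Secondary Analysis 5, base the between-arm comparison on those answers. Count every event in the period, whether or not it was already disclosed at Week 2, Week 8 or a group session. Do not drop events first disclosed there, for the reason in Step 5.
3. **Source of report.** Add this field to the event CRF and tabulate all events by arm and source, without a test.
4. **Stated limitations.** Say that extra disclosure in the counseling sessions held at Weeks 4 and 12, and tracing of missed visits in one arm only, remain.
5. **Reconcile the documents.** Appendix 4 marks SAE assessment at four visits, the procedure lists in Protocol 8.3 name SAE recording only at Week 12, and no assessment of events of special interest is scheduled.

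The cost is one short question, one CRF field and revised wording; the compared count then relies on recall. No visits are added, and recording of events and the response to them are unchanged.

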Statistical Analysis Plan

Title: Friendship Bench Mental Health Intervention for Adolescent Girls and Young Women in South African PrEP Delivery Settings

NCT05664490

Date Created: 15 January 2024 **Last Updated:** 29 July 2024 Drafted by: [name] MPH; [name]; [name]

Statistical Team

University of California San Francisco, San Francisco, USA

University of the Witwatersrand, Johannesburg, South Africa

Table of Contents

Background and Rationale	. 3
Study Objectives and Hypothesis	. 3
Study Design	. 4
Schema	. 5
Overview of Study Design	. 7
Sample size and power calculations	. 8
Data Analysis	. 8

Background and Rationale

The purpose of this study is to adapt and test the Friendship Bench for South African adolescent girls and young women (AGYW) attending PrEP services, using a hybrid effectiveness-implementation trial.

The Friendship Bench is an ideal starting point for treating mild-to-moderate symptoms of common mental disorders among AGYW in PrEP delivery settings, given that it was designed for and tested in a similar African context. The proposed study will test and optimize the Friendship Bench for AGYW with mental health needs in South African/PrEP programs ("Youth Friendship Bench SA").

Study Objectives and Hypotheses

The co-primary objectives of this study are:

- To compare the proportion of young South African women who adhere well to PrEP (based on tenofovir [TFV] levels from a urine point-of-care [POC] assay) between those receiving the Youth Friendship Bench SA plus standard-of-care (SOC) mental health services versus receipt of standard-of-care services alone, after 3 months
- To compare the proportion of young South African women with reduced symptoms of common mental disorders (based on SRQ-20 score) between those receiving the Youth Friendship Bench SA plus standard-of-care mental health services versus receiving standard-of-care services alone, after 3 months

The secondary objectives of this study are:

- To compare the proportion of young South African women who adhere well to PrEP (based on tenofovir [TFV] levels from a urine point-of-care [POC] assay) between those Youth Friendship Bench SA, Version 1.030August 202222receiving the Youth Friendship Bench SA plus standard-of-care mental health services versus receipt of standard-of-care services alone, after 4 weeks.
- To assess the correlates of PrEP adherence, after adjusting for study arm, including sociodemographic factors and psychosocial and behavioral characteristics.
- To assess the correlates of symptoms of common mental disorders, after adjusting for study arm, including sociodemographic factors and psychosocial and behavioral characteristics.
- To qualitatively explore the acceptability, feasibility, and appropriateness of the Youth Friendship Bench SA intervention and the POC TFV urine assay.
- To monitor and describe the occurrence of serious adverse events over the study (defined as those events that result in death, are life-threatening, require inpatient hospitalization or prolongation of existing hospitalization, and/or result in persistent or significant disability/incapacity) plus adverse events of special interest (reports of self-harm or selfinjury).

The exploratory objectives of this study are:

- To explore mediators and moderators of the Youth Friendship Bench SA intervention effect on PrEP adherence.
- To explore mediators and moderators of the Youth Friendship Bench SA intervention effect on symptoms of common mental disorders.

Study Design

This is as single-site effectiveness-implementation randomized controlled trial. 110 participants are planned and will be consented to have 12 weeks of follow-up. All participants will be offered PrEP by clinic personnel as part of standard PrEP prescribing practices, and PrEP delivery (including PrEP readiness assessment, HIV testing, PrEP adherence counseling that is not part of the urine point-of-care drug-level feedback, and PrEP prescribing) is not considered a research procedure.

Each participant will be randomized in a 1:1 ratio to receive either standard-of-care plus our Youth Friendship Bench SA mental health intervention package or standard-of-care alone. Our co-primary endpoints are PrEP adherence assessed using tenofovir detected in a urine POC assay performed at the Week 12 study visit and symptoms of common mental disorders assessed using the SRQ-20 at the Week 12 visit. All participants will also receive PrEP adherence counseling based on results of their urine POC TFV assay at the Week 4 and 12 visits ("druglevel feedback counseling"), in addition to their standard-of-care or Youth Friendship Bench SA services.

Standard-of-care mental health services: As specified in the Adult Primary Care Guidelines,108standard-of-care services include a 2-item symptom assessment at enrollment and a brief screen about whether their mental health symptoms have changed at Week 4and Week 12, to align with PrEP refill schedule. Symptom assessment is to be followed by escalation and referral for mental health care assessment by a trained health care professional (e.g., social worker, psychologist, or medical doctor) as needed. This assessment is administered by a counselor or nurse or could be self-administered.

Youth Friendship Bench SA + Standard-of-Care: The Youth Friendship Bench SA intervention includes: five individual counseling sessions conducted at Enrollment, Week 2, Week 4, Week 8, and Week 12; one optional in-person or WhatsApp-based group counseling session between Week 8 and Week 12; optional remote counseling sessions; and optional one-way SMS messages to provide reminders about upcoming visits. Individual counseling sessions will last up to 60 minutes. Group counseling sessions will last up to 120 minutes. A subset of up to 30 AGYW will also be recruited to participate in gualitative in-depth interviews to be conducted between Weeks 4 and 12 of study participation. These interviews will explore their perceptions of the acceptability, feasibility, and appropriateness of the Youth Friendship Bench SA and standard-ofcare services. We will also ask about perceptions around the use of a urine POC assay for PrEP adherence assessment and drug-level feedback counseling. Throughout the study period (up to 2times per month), trained social scientist interviewers will observe participants' waiting room discussions and comfort in the clinic, clinic flow, and the clinic environment for AGYW. They will record field notes during these observations to capture key information and inform future Youth Friendship Bench SA and standard-of-care mental health service delivery. Screening data will be reviewed to determine participant eligibility. Participants who meet all inclusion criteria and none of the exclusion criteria will be entered into the study. The total duration of participant participation will be three months. We will escalate any participants who report self-harm, worsening symptoms of common mental disorders or psychiatric distress, and/or new presentation of somatic symptoms for referral and linkage to additional psychotherapy or pharmacotherapy as needed. The total duration of the study is expected to be three years.

Schema

Rationale:	Adolescent girls and young women (AGYW) at risk of HIV in sub-Saharan Africa, frequently (20-50%) have symptoms of common mental disorders, including depression, anxiety, and stress. These symptoms are associated with suboptimal adherence to HIV pre-exposure prophylaxis (PrEP), a highly effective HIV prevention approach. In this project, the team seeks to address poor mental health and consequent impacts on PrEP adherence and among AGYW at risk of HIV by testing an evidence-based mental health intervention (the Youth Friendship Bench SA) adapted for PrEP delivery programs.
Co-Primary Objectives:	To compare the proportion of young South African women who adhere well to PrEP (based on tenofovir levels detected in a point-of-care [POC] urine assay) between those receiving the Youth Friendship Bench SA plus standard-of-care mental health services versus receipt of standard-of-care mental health services alone, after 3 months. To compare the proportion of young South African women with reduced symptoms of common mental disorders (based on SRQ-20 score) between those receiving the Youth Friendship Bench SA plus standard-of-care mental health services versus receiving standard-of-care services alone, after 3 months
Design:	This is a randomized hybrid implementation-effectiveness trial which will be conducted in a real-world healthcare setting. Eligible women who accept open- label daily oral PrEP (n=110) will be enrolled and randomized to either the Youth Friendship Bench SA intervention (plus standard-of-care mental health services as needed) or standard-of-care mental health services alone. Randomization will be conducted in a 1:1 ratio with randomly sized blocks of ≤10. Participants randomized to the Youth Friendship Bench SA will be offered up to 5 60-minute counseling sessions conducted at enrollment, Week 2, Week 4, Week 8, and Week 12 and 1 optional group counseling session between
	their Week 8 and 12 visits. All counseling will be conducted by peer lay counselors, who are young women between the ages of 24-30 years. Lay counselors will receive a one-week training course prior to study activation and will be supervised weekly by a trained research psychologist. Participants will have the option to complete counseling sessions remotely via phone and to receive SMS reminders about upcoming clinic visits.
	Standard-of-care (SOC) mental health services will be provided in accordance with the South African Adult Primary Care Guidelines and include a brief depression symptom assessment at all visits administered by a counselor or nurse. All clients who screen positive will be referred for further assessment by a clinic social worker, who may refer the client for psychotherapy or pharmacotherapy as needed. All participants irrespective of study arm will receive further assessment by clinic staff (social worker, nurse, etc.) if they report self-harm, somatic symptoms of mental health distress, or other psychiatric symptoms. Eligible

	participants in the Youth Friendship Bench SA arm may receive the intervention in addition to any recommended SOC services if they are eligible.
	All participants will be offered PrEP in accordance with national PrEP guidelines as part of routine care. We will also provide all participants with brief PrEP adherence counseling based on their urine POC assay results at the Week 4 and Week 12 visits. This adherence counseling will be in addition to their Youth Friendship Bench SA or standard-of-care mental health service delivery.
	All participants will be followed for three months.
	We will conduct qualitative data collection with a purposive sample of up to30 AGYW in the trial (between Week 4 and Week 12) and 15 health care providers and key informants to characterize themes around acceptability, appropriateness, and feasibility of Youth Friendship Bench SA and the urine POC TFV assay. We will also conduct ethnographic clinic observations throughout the study period (to 2 times per month).
Study Population:	HIV-uninfected women ages 18-25 in Johannesburg, South Africa, who have symptoms of common mental disorders as evidenced by a score greater than or equal to 7 on the SRQ-20.
Study Size:	Up to 110 women who accept PrEP will be consented and randomized
Outcome measures:	We have co-primary outcomes: PrEP adherence and common mental disorder symptoms. The PrEP adherence primary outcome is the proportion with PrEP adherence at Month 3, defined as tenofovir (TFV) concentrations ≥1500 ng/mL in urine measured using a urine POC assay. We will also assess the short-term effect of the Youth Friendship Bench SA intervention on PrEP adherence using the urine POC assay at the Week 4 visit.
	The mental health related primary outcome is the proportion with reduced symptoms of common mental disorders (SRQ-20 scores <7) at Month 3, measured using the SRQ-20
Study Duration:	Approximately 36 months, including submissions to Institutional Review Boards (IRBs) and study start up activities (6 months), recruitment and enrollment (12 months), participant follow up (3 months following the last enrolled participant), and data analysis (remaining time through 36 months).
Study Site:	Ward 21 public clinic in Johannesburg, South Africa.

Overview of Study Design

Figure 1. Study schema for the evaluation of the Youth Friendship Bench SA counseling intervention

Sample size

We will randomize 110 AGYW in a 1:1 ratio to either our adapted intervention or standard-of-care mental health services over a 12-month study period (approximately 9-10 AGYW enrolled per month). Based on current levels of AGYW receiving PrEP at the public health clinic in Johannesburg, and reporting symptoms of common mental disorders and receiving referral services, we will likely need to screen approximately 18-20 AGYW per month to meet our enrollment targets. Based on prior PrEP studies with AGYW in this setting (HPTN 082, PrEP SMART, POWER), we expect to retain 85-90% of AGYW through three months of follow-up.

Power calculations

For our primary outcome of PrEP adherence, if we assume 40% PrEP adherence in the standardof-care arm (as was seen in the HPTN 082 trial with AGYW in this setting) and an alpha of 0.05, we will have 80% power to detect at least a 20% difference in the proportion with adherence between arms.

For our primary outcome of common mental disorder symptoms, if we assume 50% prevalence of symptoms of common mental disorders (again, as was seen in the HPTN 082 and PrEP SMART trials) and an alpha of 0.05, we will have 80% power to detect at least a 25% difference in the proportion with symptoms of common mental disorders between arms.

Data Analysis

Co-Primary Analysis 1: To compare the proportion of young South African women who adhere well to PrEP (based on tenofovir [TFV] levels from a urine point-of-care [POC] assay) between those receiving the Youth Friendship Bench SA plus standard-of-care (SOC) mental health services versus receipt of standard-of-care services alone, after 3 months

Analysis population: South African AGYW participants enrolled and randomized in a 1:1 ratio to either the Youth Friendship Bench SA plus SOC intervention or the SOC services alone arm.

- For an intent-to-treat analysis, we will include all randomized participants.
- For a per protocol analysis, we will include all randomized participants who received a full dose of the Youth Friendship Bench SA plus SOC intervention or SOC services alone, as specified below.

Outcome: proportion of AGYW with PrEP adherence at Week 12, defined as tenofovir (TFV) concentrations ≥1500 ng/mL in urine measured using a urine POC assay.

• We will utilize urine TFV levels to assess PrEP dosing in the prior 4-7 days.

Predictor(s) of interest: Randomized intervention arm, either the Youth Friendship Bench SA plus SOC or SOC services alone groups.

Covariate(s) of interest: For the per protocol analysis, the regression model will adjust for potential confounding from covariate characteristics assessed at baseline and follow-up, which may include:

• Sociodemographic characteristics; sexual behaviors; gender-based violence (GBV); symptoms of common mental disorders; self-esteem; and level of engagement with the intervention.

Measures of intervention use for per protocol analysis:

- Received the Youth Friendship Bench SA plus SOC intervention: 1 = received 4-5 sessions of the intervention (not including the group session). 0 = received less than 4 sessions of the intervention
- Received SOC services alone: 1 = received 4-5 sessions of SOC services alone. 0 = received less than 4 sessions of SOC services alone.

Statistical analyses:

- 1) We will compute descriptive statistics to describe the full study population of randomized individuals at baseline and to describe retention over time in both arms of the intervention. We will also summarize reasons for discontinuing PrEP.
- 2) We will compute descriptive statistics for missing data, including the pattern of missingness across visits for both arms of the intervention, and factors associated with missingness. All information from participants with missing data will be examined to determine if any pattern is evident that would account for the missingness.
